3.1 Subject Selection

The subjects in this study will be adult male or female subjects with scleroderma who have skin thickening in an area suitable for repeat biopsy.

The investigator (physician) or qualified designee will discuss the study with a subject/the legal representative of a subject who is considered a potential candidate for the study. If there is interest in participating in the study, the subject/legal representative will be provided with the informed consent form. The investigator or designee will address any questions and/or concerns that the subject/legal representative may have and, if there is continued interest, will secure written informed consent for participation in the study. Written informed consent and Health Insurance Portability and Accountability Act (HIPAA) authorization (applies to covered entities in the US only) will be obtained prior to conducting any protocol-related procedures, including screening evaluations or medication washouts.

3.1.1 Inclusion Criteria

Subjects must meet *all* of the following criteria:

- 1) Male or female subjects ≥ 18 years of age at the time of the first dose of MEDI-546;
- 2) Written informed consent and HIPAA authorization (applies to covered entities in the US only) obtained from the subject or subject's legal representative;
- 3) Must fulfill the American Rheumatism Association (American College of Rheumatology) preliminary classification criteria for systemic sclerosis ([Appendix 1](#));
- 4) Has at least moderate skin thickening (score of at least 2 by modified Rodnan Total Skin Score [mRTSS]) in at least one area suitable for repeat biopsy, such as arms, legs, or trunk;
- 5) Women, unless surgically sterile (including tubal ligation) or at least 2 years post-menopausal, must use an effective method of avoiding pregnancy (including oral, injectable, transdermal, or implanted contraceptives, intrauterine device, diaphragm with spermicide, cervical cap, abstinence, and sterile sexual partner) in addition to the use of condoms (male or female condoms with spermicide) from signing of the informed consent through the end of the study. Cessation of birth control after this point should be discussed with a responsible physician. Men, unless surgically sterile, must likewise practice 2 effective methods of birth control (condom with spermicide

or abstinence) and must use such precautions from Study Day 0 through the end of the study;

- 6) Ability to complete the study period, including follow-up period through a maximum of Study Day 105; and
- 7) Willing to forego other forms of experimental treatment during study.

3.1.2 Exclusion Criteria

Subjects must have *none* of the following:

- 1) History of allergy or reaction to any component of the MEDI-546 formulation;
- 2) Forced vital capacity (FVC) < 60% predicted, diffusing capacity for carbon monoxide (DL_{CO}) < 40% predicted, pulmonary hypertension requiring treatment with endothelin receptor antagonists or prostacyclin analogues, scleroderma renal crisis within the last year, or medically significant malabsorption;
- 3) Have received the following medications within 28 days before entry:
 - Cyclophosphamide at any dose
 - Systemic cyclosporine at any dose
 - Thalidomide at any dose
 - Hydroxychloroquine > 600 mg/day
 - Mycophenolate mofetil > 3 g/day
 - Methotrexate > 25 mg/week
 - Azathioprine > 3 mg/kg/day;
- 4) Have received leflunomide > 20 mg/day within 6 months before entry;
- 5) Have received fluctuating doses of the following within 28 days before entry:
 - Antimalarials
 - Mycophenolate mofetil
 - Methotrexate
 - Leflunomide
 - Azathioprine;
- 6) Have received prednisone > 20 mg/day or in fluctuating doses within 14 days before entry;
- 7) Have received fluctuating doses of nonsteroidal anti-inflammatory drugs (NSAIDs) within 14 days before entry;

- 8) Treatment with any investigational drug therapy within 28 days before entry into the study, B cell-depleting therapies within 12 months before entry, or biologic therapies within 30 days or 5 half-lives of the biologic agent, whichever is longer, before entry into the study;
- 9) In the investigator's opinion, evidence of clinically significant active infection, including ongoing, chronic infection, within 28 days before entry;
- 10) A history of severe viral infection as judged by the investigators, including severe infections of either cytomegalovirus (CMV) or the herpes family such as disseminated herpes, herpes encephalitis, ophthalmic herpes;
- 11) Herpes zoster infection within 3 months before entry;
- 12) Evidence of infection with hepatitis B or C virus, or human immunodeficiency virus (HIV)-1 or HIV-2, or active infection with hepatitis A, as determined by results of testing at screening;
- 13) Vaccination with live attenuated viruses within 28 days before entry;
- 14) Pregnancy (women, unless surgically sterile or at least 2 years post-menopausal, must have a negative serum pregnancy test within 28 days before receiving MEDI-546 and a negative urine pregnancy test on days of MEDI-546 administration before receiving MEDI-546);
- 15) Breastfeeding or lactating women;
- 16) History of primary immunodeficiency;
- 17) History of alcohol or drug abuse < 1 year prior to entry;
- 18) History of cancer except basal cell carcinoma or in situ carcinoma of the cervix treated with apparent success with curative therapy > 1 year prior to entry.
- 19) History of active tuberculosis (TB) infection or latent TB infection without completion of an appropriate course of treatment;
- 20) Newly positive TB skin test (defined as a reaction ≥ 10 mm in diameter if not on systemic immunosuppressive medication or ≥ 5 mm if on systemic immunosuppressive medication) without concomitant prophylactic therapy;
- 21) Elective surgery planned from the time of signing of the informed consent through end of study;
- 22) At screening blood tests (within 28 days before entry), any of the following:
 - Aspartate aminotransferase (AST) > 2.5 x upper limit of the normal range (ULN), unless due to documented myositis
 - Alanine aminotransferase (ALT) > 2.5 x ULN, unless due to documented myositis.
 - Creatinine > 4.0 mg/dL
 - Neutrophils < 1,500/mm³

- Platelet count < 50,000/mm³;
- 23) History of any disease, evidence of any current disease (other than scleroderma), any finding upon physical examination, chest x-ray, or any laboratory abnormality that, in the opinion of the investigator or medical monitor, may compromise the safety of the subject in the study or confound the analysis of the study; or
- 24) Any employee of the research site who is involved with the conduct of the study.
- 25) History of vasculitis (vasculopathy of scleroderma is not a vasculitis)

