3.2 Enrollment and Study Entry

A subject is considered enrolled into the study once written informed consent is obtained. A subject is considered entered into the study at the time of the investigational product administration (Study Day 0).

Once informed consent is obtained, a subject identification number (SID) will be assigned by a central system (eg, an interactive voice response system, IVRS) and the screening evaluations may begin. This number will be used to identify the subject during the screening process and throughout study participation.

Enrolled subjects will be screened by investigators or qualified designees to assess eligibility for entry into the study. A master log will be maintained of all enrolled subjects and will document all screening failures (ie, subjects who are consented and enrolled but not entered), including reason for screening failure.

Subjects who fail to meet all eligibility criteria, who decline further participation, or who are lost to follow-up will not proceed to entry.

The procedure for study entry is as follows:

- The subject arrives at the clinic or hospital for the Study Day 0 visit;
- The investigator or designee confirms that written informed consent has been obtained and that the subject meets eligibility criteria;
- The investigator or designee calls the IVRS and provides the SID and subject's baseline characteristic(s) used to verify that it is the same subject; and
- A confirmatory fax with this information is sent to the investigator/designee.

MEDI-546 must be administered within 8 hours after preparation. If the dose is not administered within 8 hours, a new dose must be prepared using a new vial. Subjects are considered evaluable for safety if they receive MEDI-546 and complete the required

evaluations through Study Day 7 or if they discontinue MEDI-546 for safety reasons. In addition, subjects are considered evaluable for the exploratory endpoints if they complete Study Day 28. Nonevaluable subjects may be replaced for reasons other than safety to maintain the stipulated cohort sizes in each dose cohort.

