 - Exploratory correlative studies and storage (serum)

- DNA sample (optional)
- 7) Assess health assessment questionnaire-disability index (HAQ-DI) with scleroderma numeric rating scales (may be done up to 72 hours prior to dosing and preferably prior to the mRTSS and the European disease activity index [DAI] and MEDI-546 administration)
- 8) Assess mRTSS (may be done up to 72 hours prior to dosing)
- 9) Assess European DAI (may be done up to 72 hours prior to dosing)
- 10) Skin biopsy for type I IFN-inducible genes and exploratory analyses (prior to MEDI-546 administration and may be done anytime between signing of the informed consent and Study Day 0)
- 11) Monitor vital signs within 60 minutes before administration of MEDI-546
- 12) **Administration of MEDI-546**
- 13) Monitor vital signs about every 15 minutes during infusion, immediately after the end of the infusion, and about every 30 minutes after the end of the infusion for 2 hours or until stable, whichever is later. Monitor blood pressure and heart rate prior to discharge from the study site.
- 14) Blood collection at 0.5 hours post end of infusion
 - MEDI-546 serum concentration
 - Receptor occupancy
- 15) Monitor for AEs and SAEs

Study Day 1

All Dose Cohorts

- 1) Monitor vital signs
- 2) Monitor for AEs and SAEs
- 3) Record concomitant medications
- 4) Collection of blood
 - MEDI-546 serum concentration
 - Receptor occupancy analysis
 - Type I IFN-inducible genes, exploratory analyses, and storage
 - Exploratory correlative studies and storage (serum)

Study Day 7 (\pm 1 day)

All Dose Cohorts

- 1) Monitor vital signs
- 2) Monitor AEs and SAEs
- 3) Record concomitant medications
- 4) Collection of blood and urine prior to MEDI-546 administration, if applicable
 - Serum chemistry
 - Hematology
 - Urinalysis
 - MEDI-546 serum concentration
 - Receptor occupancy analysis
 - Type I IFN-inducible genes, exploratory analyses, and storage
 - Exploratory correlative studies and storage (serum)

Dose Cohorts 1-5 and 9 only

- 5) Skin biopsy for type I IFN-inducible genes and exploratory studies

Dose Cohorts 6-8 only

- 6) Urine β HCG prior to MEDI-546 administration
- 7) Monitor vital signs within 60 minutes before administration of MEDI-546
- 8) **Administration of MEDI-546**

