3.6.14 Pharmacokinetic and Pharmacodynamic Evaluations

The following PK and PD assessments will be made during the study:

- Serum will be collected at every study visit for the determination of MEDI-546 serum concentration. On Study Day 0 for both single- and multiple-dose administration and on Study Day 21 for multiple dose administration, PK sampling will occur pre-dose and at 0.5 hour post end of infusion. Specific procedures for sample collection, processing, storage, and shipment can be found in a separate laboratory manual provided to sites.
- Whole blood will be collected at visits specified in the study schedule ([Table 3.5-1](#) and [Table 3.5-2](#)) to measure the level of receptor occupancy (flow cytometry measurement of the binding of labeled MEDI-546 in the presence of dosed levels of MEDI-546) and total IFNAR levels (using a separate anti-IFNAR1 antibody that binds to a distinct epitope from MEDI-546). On Study Day 0 for both single- and multiple-dose administration and on Study Day 21 for multiple dose administration, receptor occupancy sampling will occur pre-dose and at 0.5 hour post end of infusion. Specific procedures for sample collection, processing, storage, and shipment can be found in a separate laboratory manual provided to sites.
- Type I IFN-inducible genes also will be used to measure the PD of MEDI-546. Whole blood samples will be used to analyze the effects of MEDI-546 on levels of mRNA for type I IFN-inducible genes. This analysis is performed using Affymetrix whole genome expression array and taqMan-based assay on selected panel of genes. Whole blood will be collected at visits specified in the study schedule. Specific procedures for sample collection, processing, storage, and shipment can be found in a separate laboratory manual provided to sites.
- Skin biopsies will also be collected for type I IFN-inducible genes and exploratory studies. Baseline skin biopsy (one 6mm or two 3mm or two 4mm) should be obtained prior to MEDI-546 administration on Study Day 0 and can be obtained anytime between screening and MEDI-546 administration. Sites will be given specific instructions for sample collection, processing, storage, and shipment.

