5.5.3 Pharmacodynamics

The level of receptor occupancy will be determined by flow cytometry as a measure of the binding of labeled MEDI-546 in the presence of dosed levels of MEDI-546. Total type I IFNAR levels will be assessed using a separate anti-IFNAR1 antibody that binds to a distinct epitope from MEDI-546.

The level of expression of type I IFN-inducible genes will be determined in whole blood and skin mRNA, using Affymetrix technology. Results will be listed by dose group with mean and individual results at different time points. Changes from baseline will be described and PD assessed. Relationships between receptor occupancy and inhibition of type I IFN gene signature will be explored.

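### The baseline skin biopsy may be taken before the 14-day stable corticosteroid period begins, so a permitted pre-dose steroid change can fall between the two biopsies and partly confound the skin IFN-signature change

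*Protocol*

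**What the plan says.** **Background treatment.** Exclusion 6 (Protocol 3.1.2) bars subjects who "Have received prednisone > 20 mg/day or in fluctuating doses within 14 days before entry". Exclusion 7 sets the same period for NSAIDs: "Have received fluctuating doses of nonsteroidal anti-inflammatory drugs (NSAIDs) within 14 days before entry". Section 3.2 defines entry as dosing on Study Day 0. Section 3.4.5 asks, so far as possible, for constant NSAID and oral corticosteroid doses from 14 days before Day 0 to the end of follow-up. For antimalarials, mycophenolate, methotrexate, leflunomide and azathioprine the period is twice as long: "Have received fluctuating doses of the following within 28 days before entry".

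**Biopsy.** Section 3.5, Study Day 0 item 10, places the baseline skin biopsy "prior to MEDI-546 administration and may be done anytime between signing of the informed consent and Study Day 0". Section 3.6.14 says that it "can be obtained anytime between screening and MEDI-546 administration". Tables 3.5-1 and 3.5-2 show one baseline biopsy and one repeat, on Day 7 for the single-dose cohorts and Day 28 for the multiple-dose cohorts.

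**Other baselines.** Section 3.5 limits the Day 0 blood samples, including the blood IFN signature, and the skin score, disease activity index and HAQ-DI to at most 72 hours before dosing.

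**Use.** Section 2.2 names the signature in involved skin as a pharmacodynamic marker under a secondary objective. Section 5.5.3 says of the analysis: "Changes from baseline will be described and PD assessed".

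**The concern.** The protocol controls corticosteroid dose from Day -14 but lets the skin baseline be taken up to two weeks before that control starts. Section 3.1 requires consent before any study procedure, "including screening evaluations or medication washouts", and Section 4.4 lists washout of an existing medication among screening procedures. Treatment changes between consent and dosing are therefore foreseen. A subject could be biopsied early in screening on a corticosteroid dose outside exclusion 6, come within it by Day -14 and be dosed, all without a protocol deviation.

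The skin comparison has one sample before and one after dosing, in planned cohorts of four (one in Cohort 1), with no control arm. A background-treatment change between the two samples cannot be separated from a drug effect by design. The blood and skin baselines could also be taken under different background treatment, which weakens comparison of the two tissues.

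**Working it through.** The plan states no figure on this point, so the check sets its windows side by side and counts days.

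**1. Windows before dosing**

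| Item | Window | Source |
|---|---|---|
| Screening | Day -28 to Day -1 | Tables 3.5-1, 3.5-2 |
| Baseline skin biopsy | consent or screening to dosing on Day 0 | 3.5 item 10; 3.6.14 |
| Prednisone and NSAID stability | Day -14 to Day 0 | 3.1.2 (6, 7); 3.4.5 |
| Stability of the five other drug classes or drugs | Day -28 to Day 0 | 3.1.2 (5); 3.4.5 |
| Blood signature, skin score, disease index | last 72 hours before dosing | 3.5 |

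Biopsy days outside the prednisone and NSAID window run from Day -28 to Day -15: 28 - 15 + 1 = 14 days, and 14/28 = 50% of the screening days. For the drugs with a 28-day rule the count is 0. The gap is thus specific to the skin biopsy combined with corticosteroids and NSAIDs. No section ties the biopsy date to the start of stable dosing or asks for a second baseline biopsy.

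**2. Interval between the two biopsies**

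- Single-dose cohorts, repeat on Day 7 ± 1: shortest 6 - 0 = 6 days, longest 8 + 28 = 36 days.
- Multiple-dose cohorts, repeat on Day 28 ± 2: shortest 26 - 0 = 26 days, longest 30 + 28 = 58 days.

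With the baseline biopsy confined to Day -14 onward, the longest intervals become 8 + 14 = 22 and 30 + 14 = 44 days, and the unprotected pre-dose days fall from 14 to 0.

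**3. What a steroid change could do (illustration only)**

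Let I be the true inhibition and d the relative change in signature caused by a steroid change alone. Then

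measured inhibition = 1 - (1 - I)(1 + d), so the error is (1 - I) × d.

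The documents give no value for d. Assuming 10% to 30% in either direction, at I = 70%:

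| d | Measured if d is positive | Measured if d is negative |
|---|---|---|
| 10% | 1 - 0.30 × 1.1 = 67% | 1 - 0.30 × 0.9 = 73% |
| 20% | 1 - 0.30 × 1.2 = 64% | 1 - 0.30 × 0.8 = 76% |
| 30% | 1 - 0.30 × 1.3 = 61% | 1 - 0.30 × 0.7 = 79% |

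The error is 3 to 9 percentage points at 70% inhibition. By the formula it is larger where true inhibition is smaller.

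**4. Who can still benefit**

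Section 1.4 reports 17 subjects enrolled and escalation through Cohort 5. Planned numbers in Cohorts 1-5 are 1 + 4 × 4 = 17, so a changed biopsy rule applies to Cohorts 6-9, 4 × 4 = 16 planned subjects.

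**The case against.** The strongest reply is that the mismatch is real but its consequence is not shown. Five parts of that reply deserve an answer.

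- **No causal link in the documents.** Nothing says that prednisone, still less an NSAID, alters the skin IFN signature, and exclusions 6-7 give no reason for requiring stability. This stands. The point is that the design permits confounding, not that confounding has occurred. The NSAID part is the weaker one.
- **Few subjects may be affected.** The schedule tables put the biopsy in the Day 0 column, so an early biopsy is permitted rather than scheduled. A problem also needs a dose change after the biopsy and before Day -14. The washout wording is general and names no drug. This stands: 14 of 28 days measures opportunity, not frequency.
- **Affected subjects can be identified.** Sections 3.4.5 and 3.6.8 have concomitant medications recorded from consent, with dose and dates, and Section 5.5.3 lists individual results. This is correct and makes flagging feasible. But analysis can only mark or drop such a subject, at 1 in 4 of a cohort each. It cannot recover a baseline taken under the right conditions.
- **Later changes remain.** Section 3.4.5 asks for stability after Day 0 only so far as possible. That is true, and aligning the biopsy removes only the pre-dose part.
- **Scope is narrow.** The primary endpoint is safety (5.4), and the blood signature has a 72-hour baseline. This also stands.

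Two stronger readings are tempting and should be resisted. A reader might infer that the skin change could reflect a steroid change instead of MEDI-546. The documents give no effect size to support that, and the assumed range shifts a 70% inhibition by 3 to 9 points without replacing it. A reader might also infer that one early biopsy could still flip the Section 5.7 criterion of at least 70% inhibition in at least three subjects and so alter the multiple-dose levels. Section 1.4 reports that this interim analysis was completed on 14 July 2010 by modelling PK and PD data across the single-dose cohorts, and Section 3.4.2 says that the levels have been modified. A footnote to Table 3.4.2-1 still allows modification, but no further dose-selection analysis is described.

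**Conclusion.** The point holds as a limited but avoidable design weakness. The biopsy window and the corticosteroid stability window do not match, no other section closes the gap, and the protocol applies tighter rules to every comparable baseline and to the other immunosuppressants. A permitted pre-dose corticosteroid change can therefore fall between the two biopsies and partly confound an uncontrolled within-subject comparison of a secondary pharmacodynamic marker.

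The size in the documents' own terms is 14 of 28 screening days. The effect on results is unknown in magnitude, direction and number of subjects; the percentages in the illustration rest wholly on an assumed steroid effect. The primary safety endpoint, the blood signature and the completed dose selection would not be changed by the fix. It is worth making because it is cheap, not because the skin results are shown to be wrong.

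**What to change.** **For subjects still to be entered (Cohorts 6-9).** Reconcile Section 3.5 (Study Day 0 item 10) and Section 3.6.14 with exclusions 6-7 and Section 3.4.5: require the baseline skin biopsy within the 14 days before Day 0, inside the existing stable-dose period. No dose limit or eligibility rule needs to change.

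**For biopsies already taken.** Use the concomitant medication records to flag any baseline biopsy followed by a corticosteroid change, and show skin-signature change from baseline with and without the flagged subjects.

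**Cost.** Sites have less flexibility in scheduling the same single biopsy, and later cohorts will have a tighter baseline window than earlier ones, which should be noted when cohorts are compared. No procedure or subject is added. Dose changes after Day 0 are not addressed.

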3.2 Enrollment and Study Entry

A subject is considered enrolled into the study once written informed consent is obtained. A subject is considered entered into the study at the time of the investigational product administration (Study Day 0).

Once informed consent is obtained, a subject identification number (SID) will be assigned by a central system (eg, an interactive voice response system, IVRS) and the screening evaluations may begin. This number will be used to identify the subject during the screening process and throughout study participation.

Enrolled subjects will be screened by investigators or qualified designees to assess eligibility for entry into the study. A master log will be maintained of all enrolled subjects and will document all screening failures (ie, subjects who are consented and enrolled but not entered), including reason for screening failure.

Subjects who fail to meet all eligibility criteria, who decline further participation, or who are lost to follow-up will not proceed to entry.

The procedure for study entry is as follows:

- The subject arrives at the clinic or hospital for the Study Day 0 visit;
- The investigator or designee confirms that written informed consent has been obtained and that the subject meets eligibility criteria;
- The investigator or designee calls the IVRS and provides the SID and subject's baseline characteristic(s) used to verify that it is the same subject; and
- A confirmatory fax with this information is sent to the investigator/designee.

MEDI-546 must be administered within 8 hours after preparation. If the dose is not administered within 8 hours, a new dose must be prepared using a new vial. Subjects are considered evaluable for safety if they receive MEDI-546 and complete the required

evaluations through Study Day 7 or if they discontinue MEDI-546 for safety reasons. In addition, subjects are considered evaluable for the exploratory endpoints if they complete Study Day 28. Nonevaluable subjects may be replaced for reasons other than safety to maintain the stipulated cohort sizes in each dose cohort.

If there is a possible safety signal from the analysis of safety information for a particular dose cohort (Dose Cohorts 2-9 only) that does not warrant discontinuation but does warrant further investigation (prior to dose escalation for Dose Cohorts 2-7), then the sponsor may add 4 subjects to the dose cohort for a maximum of 8 subjects in the dose cohort. A maximum of 2 dose cohorts may be expanded to a total of 8 subjects each. If a possible safety signal occurs subsequent to expansion of 2 dose cohorts to a maximum of 8 subjects each, then the study will be terminated. In addition, Dose Cohorts 2-9 may be expanded by up to 2 additional subjects each if eligible subjects are already in screening at the time 4 subjects have been entered into the dose cohort and there is no possible safety signal to warrant expansion of the dose cohort to a maximum of 8 subjects. Therefore, the maximum number of subjects allowed in the study is 53 ($29 + 8 [4 \times 2] + 12 [2 \times 6]$).

Decisions regarding dose escalation will be made by the medical monitor based on the review of all cumulative safety information from the stipulated number of subjects in the preceding lower dose cohort through Study Day 7 for single-dose cohorts (Dose Cohorts 1-5) or Study Day 28 for multiple-dose cohorts (Dose Cohorts 6 and 7) and all cumulative safety data available in all other cohorts. The SMC, which includes physicians external to MedImmune, also will review cumulative safety surveillance data throughout the study and can make recommendations regarding the study progression. The Safety Monitoring Committee (SMC) can stop study entry and dosing as it deems necessary.

